#### **7.3.1.2.2. Overactive Bladder Symptom Score (OABSS)**

Symptoms of frequency, nocturia, urinary urgency, and urge incontinence will be assessed with OABSS in accordance with the study schedule.

OABSS was developed by Honma et al. as questionnaire to comprehensively assess OAB symptoms, and its appropriateness was verified in Japanese OAB patients. [The Japanese Continence Society, 2005; Honma, 2006]

Investigators/sub-investigators or the persons assisting with the trial will provide an OABSS questionnaire including 4 questions for subjects and instruct subjects to select the one most appropriate answer for each question.

#### **7.3.1.2.3. Treatment Benefit Scale (TBS)**

Treatment benefit of GSK1358820 will be assessed with TBS in accordance with the study schedule. TBS was developed by Colman et al. as questionnaire for a patient-based treatment benefit assessment for OAB, and its appropriateness was verified in OAB patients. [Colman, 2008]

Investigators/sub-investigators or the persons assisting with the trial will provide a questionnaire including 1 question on TBS for subjects and instruct subjects to select the one most appropriate answer for each question.

Answer the following question after considering your present symptoms (issues of the urinary system, urine incontinence ) in comparison with those before treatments in this study.

In the course of the treatment, my symptoms is:

1. greatly improved
2. improved
3. not changed
4. worsened

### **7.4. Safety**

Planned time points for all safety assessments are listed in the Time and Events Table (Section 7.1.). Additional time points for safety tests may be added during the course of the study based on newly available data to ensure appropriate safety monitoring.

#### **7.4.1. Adverse Events (AE) and Serious Adverse Events (SAEs)**

The definitions of an AE or SAE can be found in Appendix 3.

The investigator and their designees are responsible for detecting, documenting and reporting events that meet the definition of an AE or SAE.

##### **7.4.1.1. Time period and Frequency for collecting AE and SAE information**

- AEs will be collected from the start of Study Treatment until the study exit (see Section 7.4.1.3), at the timepoints specified in the Time and Events Table (Section 7.1.).
- Medical occurrences that begin prior to the start of study treatment but after obtaining informed consent may be recorded on the Medical History/Current Medical Conditions section of the CRF.
- Any SAEs assessed as related to study participation (e.g., protocol-mandated procedures, invasive tests, or change in existing therapy) or related to a GSK product will be recorded from the time a subject consents to participate in the study up to study exit.
- All SAEs will be recorded and reported to GSK within 24 hours, as indicated in Appendix 3.
- Investigators are not obligated to actively seek AEs or SAEs in former study subjects. However, if the investigator learns of any SAE, including a death, at any time after a subject has been discharged from the study, and he/she considers the event reasonably related to the study treatment or study participation, the investigator must promptly notify GSK.

NOTE: The method of recording, evaluating and assessing causality of AEs and SAEs plus procedures for completing and transmitting SAE reports to GSK are provided in Appendix 3.

##### **7.4.1.2. Method of Detecting AEs and SAEs**

Care will be taken not to introduce bias when detecting AEs and/or SAEs. Open-ended and non-leading verbal questioning of the subject is the preferred method to inquire about AE occurrence.

Appropriate questions include:

- “How are you feeling?”
- “Have you had any (other) medical problems since your last visit/contact?”
- “Have you taken any new medicines, other than those provided in this study, since your last visit/contact?”

##### **7.4.1.3. Follow-up of AEs and SAEs**

After the initial AE/SAE report, the investigator is required to proactively follow each subject at subsequent visits/contacts. All SAEs, and non-serious AEs of special interest (as defined in Section 4.6.1.) will be followed until resolution, until the condition stabilizes, until the event is otherwise explained, or until the subject is lost to follow-up (as defined in Section 5.5.). Further information on follow-up procedures is given in Appendix 3.

##### **7.4.1.4. Cardiovascular and Death Events**

For any cardiovascular events detailed in Appendix 3 and all deaths, whether or not they are considered SAEs, specific Cardiovascular (CV) and Death sections of the CRF will be required to be completed. These sections include questions regarding cardiovascular (including sudden cardiac death) and non-cardiovascular death.

The CV CRFs are presented as queries in response to reporting of certain CV MedDRA terms. The CV information should be recorded in the specific cardiovascular section of the CRF within one week of receipt of a CV Event data query prompting its completion.

The Death CRF is provided immediately after the occurrence or outcome of death is reported. Initial and follow-up reports regarding death must be completed within one week of when the death is reported.

#### **7.4.1.5. Regulatory Reporting Requirements for SAEs**

Prompt notification by the investigator to GSK of SAEs related to study treatment (even for non-interventional post-marketing studies) is essential so that legal obligations and ethical responsibilities towards the safety of subjects and the safety of a product under clinical investigation are met.

GSK has a legal responsibility to notify both the local regulatory authority and other regulatory agencies about the safety of a product under clinical investigation. GSK will comply with country specific regulatory requirements relating to safety reporting to the regulatory authority, Institutional Review Board (IRB)/Independent Ethics Committee (IEC) and investigators.

Investigator safety reports are prepared for suspected unexpected serious adverse reactions according to local regulatory requirements and GSK policy and are forwarded to investigators as necessary.

An investigator who receives an investigator safety report describing a SAE(s) or other specific safety information (e.g., summary or listing of SAEs) from GSK will file it with the IB and will notify the IRB/IEC, if appropriate according to local requirements.

#### **7.4.2. Pregnancy**

- Details of all pregnancies in female subjects and if indicated female partners of male subjects will be collected after the start of dosing and until the study exit.
- If a pregnancy is reported then the investigator should inform GSK within 2 weeks of learning of the pregnancy and should follow the procedures outlined in Appendix 4.

#### **7.4.3. Physical Exams**

- A complete physical examination will include, at a minimum, assessment of the Cardiovascular, Respiratory, Gastrointestinal and Neurological systems. Height and weight will also be measured and recorded.
- Investigators (or subinvestigator) should pay special attention to clinical signs related to previous serious illnesses

#### **7.4.4. Vital Signs**

Temperature, systolic and diastolic blood pressure and pulse rate will be measured in seated position after 5 minutes rest.

#### **7.4.5. Electrocardiogram (ECG)**

Single 12-lead ECGs will be obtained at each timepoint during the study using an ECG machine that automatically calculates the heart rate and measures PR, QRS and QT. The QTc value is machine-read or manually over-read. If QTc is prolonged, QTc should be based on averaged QTc values of triplicate

electrocardiograms which are evaluated same day. Refer to Section 5.2 for exclusion criteria and Section 5.5.2 for QTc withdrawal criteria.

#### 7.4.6. Clinical Safety Laboratory Assessments

All protocol required laboratory assessments, as defined in Table 3, must be conducted in accordance with the Laboratory Manual, and Protocol Time and Events Schedule. Laboratory requisition forms must be completed and samples must be clearly labelled with the subject number, protocol number, site/centre number, and visit date. Details for the preparation and shipment of samples will be provided by the laboratory and are detailed in the SRM OR the laboratory manual. Reference ranges for all safety parameters will be provided to the site by the laboratory responsible for the assessments. If additional non-protocol specified laboratory assessments are performed at the institution's local laboratory and result in a change in subject management or are considered clinically significant by the investigator (e.g., SAE or AE or dose modification) the results must be recorded in the CRF. Refer to the SRM for appropriate processing and handling of samples to avoid duplicate and/or additional blood draws.

**Table 3     Laboratory Assessments**

Hematology	Platelet, RBC, WBC, Hemoglobin, Hematocrit, RBC morphology Differential WBC count : Neutrophil, Band, Lymphocyte, Monocyte, Eosinophil, Basophil,
Chemistry1	Bun, Creatinine, Glucose, Potassium, Sodium, Calcium, Chloride, AST (SGOT), ALT (SGPT), Alkaline phosphatase, Uric acid, Total bilirubin and direct bilirubin, Total protein, Albumin
Routine Urinalysis	
 
• Urine dipstick reagent strip tests: nitrite, leukocyte esterase
 
• Urine analysis: appearance, color, pH, specific gravity, ketones, protein, glucose, nitrite, leukocyte esterase, urobilinogen, occult blood, microscopic sediment (WBCs, RBCs, casts, bacteria, and crystals)
 
• Urine culture and sensitivity (if UTI is suggested)
 

Other Screening Tests	
 
• HBsAg and HCVAb : for subjects who receive or plan to receive immunosuppressants at screening
 
• Urine or serum hCG pregnancy test (only women of childbearing potential)
 

1. Details of Liver Chemistry Stopping Criteria and Required Actions and Follow-Up Assessments after liver stopping or monitoring event are given in Section 5.5.1 and Appendix 2.

All laboratory tests with values that are considered clinically significantly abnormal during participation in the study should be repeated until the values return to normal or baseline. If such values do not return to normal within a period judged reasonable by the investigator, the etiology should be identified and the sponsor notified.

##### 7.4.6.1. Hematology and chemistry

Hematologic and chemistry evaluations will be centrally performed at the central laboratory.

#### 7.4.6.2. Urinalysis

##### 7.4.6.2.1. Urinalysis using a urine reagent strip

Urine samples will be obtained at all study visits and a urine analysis with a urine reagent strip will be performed at each study site. If post-void residual (PVR) urine volume at scheduled visits is  $\geq 200$  mL and an additional follow-up visit occurs 1 week later, a urine analysis with a urine reagent strip will be performed (see 7.4.7 Post-void Residual (PVR) Urine Volume).

A urine analysis with a urine reagent strip will be performed to evaluate subjects for the possibility of urinary tract infection, in which the investigators/subinvestigators can receive the analysis results immediately (see 7.4.6.2.2 Urinalysis, culture and sensitivity for the definition of AE urinary tract infection). If the results of the urine analysis with a urine reagent strip suggest urinary tract infection (i.e.: positive nitrites or leukocyte esterase), treatment with antibiotics can be administered in the opinion of the investigators/subinvestigators. If the urinary tract infection is suggested, in addition to samples necessary for urinalysis which is performed at all study visit, samples for urine culture and sensitivity test must be sent to the central laboratory.

- Screening period

If a urine analysis with a urine reagent strip is positive for nitrites or leukocyte esterase or bacterial infection is confirmed by urinalysis, urine culture and sensitivity test at the central laboratory (with the presence of bacteriuria with  $10^5$  CFU [colony forming unit] per mL or more and leukocyturia with more than 5 per high power field), treatment with antibiotics will be administered in the opinion of the investigators/subinvestigators.

- Initiation of Treatment phase 1 (Week 0)

If a urine analysis with a urine reagent strip at initiation of treatment phase 1 (Week 0) is positive for nitrites or leukocyte esterase, or bacterial infection is confirmed by urinalysis, urine culture and sensitivity test at the central laboratory, treatment with antibiotics will be administered in the opinion of the investigators/subinvestigators. The subjects may return for a rescheduled initiation of treatment phase 1 (Week 0) and be treated once a dipstick confirms a negative result for infection and criteria are fulfilled (see 5.1 Inclusion Criteria and 5.2 Exclusion Criteria).

- At the time of reinjection

If a urine analysis with a urine reagent strip at the time of reinjection is positive for nitrites or leukocyte esterase, or bacterial infection is confirmed by urinalysis, urine culture and sensitivity test at the central laboratory, treatment with antibiotics will be administered in the opinion of the investigators/subinvestigators. In this case, if a subsequent urine analysis with a urine reagent strip confirms negativity for bacterial infection, the subjects who meet the criteria for reinjection are allowed to receive reinjection (see 5.3 Re-treatment Criteria).

- At a visit after the injection of the investigational drug

If a urine analysis with a urine reagent strip at a visit after the injection of the investigational drug is positive for nitrites or leukocyte esterase, or bacterial infection is confirmed by urinalysis, urine culture and sensitivity test at the central laboratory, treatment with antibiotics will be administered in the opinion of the investigators/subinvestigators.

#### **7.4.6.2.2. Urinalysis, Culture and Sensitivity**

Urinalysis, culture and sensitivity will be centrally performed at the central laboratory. A urine culture and sensitivity test will be performed when urinalysis results with a urine reagent strip are suggestive of a UTI (positive nitrites or leukocyte esterase) (see below for the definition of AE urinary tract infection).

If PVR at scheduled visits is  $\geq 200$  mL and an additional follow-up visit occurs 1 week later, urinalysis, urine culture and sensitivity test at the central laboratory will be performed (see 7.4.7 Post-void residual (PVR) urine volume).

- Definition of AE urinary tract infection

If both of the following criteria are fulfilled, urinary tract infection is recorded as an adverse event, irrespective of symptoms:

- 1) The result of urine culture is positive (with the presence of bacteriuria with  $\geq 10^5$  CFU/mL)
- 2) Leukocyturia with  $> 5$  per high power field is noted.

If subjects report urinary tract infection, which is diagnosed by a physician at a medical institution other than study sites (i.e., a family doctor or critical care physician), the results of urinalysis, urine culture, and sensitivity test should be obtained as far as possible.

#### **7.4.6.2.3. Urinary cytology**

Urinary cytology will be performed at screening period.

Urinary cytology will be centrally performed at the central laboratory.

#### **7.4.6.3. Prostate-specific antigen**

In male subjects, the level of prostate specific antigen (PSA) will be measured at screening period.

Measurement of PSA will be centrally performed at the central laboratory.

#### **7.4.6.4. Pregnancy test**

Urine pregnancy test will be performed in female subjects of childbearing potential according to the study schedule. In addition, pregnancy test is not required for female subjects of non-childbearing potential. Female subjects of non-childbearing potential are defined as postmenopausal women (women 12 months or more after menopause) or women who have undergone hysterectomy or bilateral oophorectomy. The test will be performed at each study site. Subjects are not allowed to receive the injection of the investigational drug, unless the tests at the start of treatment period 1 or at the time of reinjection are negative. If the result of urine pregnancy is suspicious, investigator (or sub-investigator) is able to conduct serum pregnancy test by central laboratory.

#### **7.4.7. Post-void residual (PVR) urine volume**

PVR urine volume will be assessed by ultrasound or bladder scan after subjects perform a voluntary void according to the study schedule. PVR urine volume can be assessed at any other time depending on clinical need. PVR measurements will not be done by catheterization.

Should a PVR urine volume indicate a clinically meaningful elevation, subjects should be asked to void once again (allowing the subjects sufficient time to void) and the PVR urine volume will then be reassessed. For subjects who have a PVR urine volume measurement repeated, only the repeat value should be recorded in the case report form (CRF).

If increased PVR is noted at a scheduled visit or at an unscheduled visit, proper procedures should be conducted according to the Guidance about the Management of PVR Urine Volume (Appendix 5).

The details of the Guidance about the Management of PVR Urine Volume are described below. Post-treatment PVR is divided into 3 categories:

- $< 200$  mL
- $\geq 200$  mL and  $< 350$  mL
- $\geq 350$  mL

The need for an additional assessment visit is assessed based on the PVR category mentioned above. The need for clean intermittent catheterization (CIC) is also dependent on the PVR as well as subject's symptoms. The objective of the guidance is to ensure that subjects are appropriately followed up and CIC is only initiated when required (while also ensuring that any unnecessary intervention is limited). However, the guidance does not preclude further actions if the investigators/subinvestigators deem the actions to be necessary.

The details are as follows:

1. PVR  $< 200$  mL

No protocol required action needs to be taken. Subjects will continue to be assessed as per the schedule of visits and procedures.

2. PVR  $\geq 200$  mL and  $< 350$  mL

If a PVR of  $\geq 200$  mL but  $< 350$  mL is identified at any post-treatment visit, the investigators/subinvestigators will assess the subject for any spontaneously reported associated symptoms (such as voiding difficulties or sensation of bladder fullness), with the resulting action to be as follows:

- a. If a subject reports associated symptoms that in the opinion of the investigators/subinvestigators require CIC to be initiated, then CIC should be initiated and managed according to the Guidance about the Management of PVR Urine Volume.
- b. If a subject does not report any associated symptoms or if they report associated symptoms that, in the opinion of the investigators/subinvestigators, do not require CIC, the subject will be seen at an additional visit 1 week later, when the PVR and any associated symptoms will be reassessed. In addition, a urine analysis with a urine reagent strip as well as urinalysis, urine culture and sensitivity test at the central laboratory will be performed. Based on the test results at this visit, the following procedures will be conducted:
  - 1) If the PVR is increasing and is associated with symptoms, that in the opinion of the investigators/subinvestigators require CIC, then CIC should be initiated and managed according to the Guidance about the Management of PVR Urine Volume.
  - 2) If the PVR is  $\geq 350$  mL then CIC should be initiated and managed according to the Guidance about the Management of PVR Urine Volume.

- 3) If the PVR is increasing but is not associated with symptoms or is associated with symptoms that in the opinion of the investigators/subinvestigators do not require CIC, then the subject will be seen 1 week later to determine if CIC has become warranted based on PVR and/or any associated symptoms. The following procedures will be conducted at this additional visit:
  - A urine reagent strip, and urinalysis, urine culture and sensitivity test at the central laboratory will be collected.
  - If the investigators/subinvestigators judge that CIC should be initiated, then CIC should be initiated and managed according to the Guidance about the Management of PVR Urine Volume.
  - If CIC is not initiated and PVR continues to increase, the investigators/subinvestigators will determine whether the subject will be followed at regularly scheduled study visits or whether additional visits should occur.
- 4) If the PVR is decreasing or is unchanged then the subject will continue to be assessed per the schedule of visits and procedures

### 3. $PVR \geq 350 \text{ mL}$

If a PVR of  $\geq 350 \text{ mL}$  is identified at any post-treatment visit (regardless of symptoms) then CIC will be initiated according to the Guidance about the Management of PVR Urine Volume.

#### **Clean intermittent catheterization (CIC)**

The following guidance should be used for the initiation and cessation of CIC in this study. Sterile, single-use intermittent catheters should be used. Indwelling catheters should not be used in this study and therefore, investigator (or sub-investigator) should discuss with medical monitors from the sponsor if an indwelling catheter is necessary.

Whether CIC is performed or not and, if CIC is performed, the dates of the initiation and completion of CIC and the reasons for CIC should be recorded in the CRF.

#### Initiation of CIC

CIC should only be initiated when one of the following criteria is fulfilled:

- PVR is  $\geq 350 \text{ mL}$  at any post treatment visit, regardless of reports of associated symptoms by subjects; or
- PVR is  $\geq 200 \text{ mL}$  and  $< 350 \text{ mL}$  and the subject spontaneously reports associated symptoms (e.g., voiding difficulties and sensation of bladder fullness) that in the opinion of the investigators/subinvestigators require CIC.

The following will occur when initiating CIC:

- 1) CIC should be performed using sterile, single-use catheters.
- 2) An adverse event of urinary retention should be recorded.
- 3) A urine analysis with a urine reagent strip as well as urinalysis, urine culture and sensitivity test at the central laboratory should be performed. In addition, these tests and analyses will be performed at scheduled visits after CIC is initiated.
- 4) The subject should be seen at a follow-up visit 1 week later, when the results of PVR measurement, associated symptoms, and a urine analysis with a urine reagent strip are

reassessed while urinalysis, urine culture and sensitivity test are performed for reassessment at the central laboratory. The investigators/subinvestigators will determine whether the subject should then be followed at regularly scheduled study visits or whether additional visits should occur.

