#### 4.6.1. Risk Assessment

Potential Risk of Clinical Significance	Summary of Data/Rationale for Risk	Mitigation Strategy
Investigational Product (IP) : GSK1358820		
Urinary tract infections (UTI)	
As the result of integrated data with 1 completed phase 2 study (191622-077), 2 completed pivotal phase3 study (191622-095 and 191622-520) and an interim cut of the long-term extension study (191622-096), the frequency of UTI as an adverse event, which was occurred in 26.4% of patients in the 100 U BOTOX group and 10.1% of patients in the placebo group (refer to IB section 5.2.4.2 Overactive Bladder).
 
The following potential factors that may have facilitated the occurrence of UTI were:
 
 
1) Elevated PVR urine volume post treatment
 
2) Initiation of clean intermittent catheterization for bladder emptying purposes when urinary retention occurred.
 
3) Patients <math>\geq</math> 65 years are more predisposed to development of UTIs overall regardless of any treatment
 
4) Cystoscopy for study drug administration procedure (intradetrusor injection) during study participation.
 
	
Patients with potential risk for these events will be excluded from this study (refer to Protocol section 5.2 exclusion criteria 4, 5, 17 and 26 )
 
Urinalysis, urine culture and sensitivity test will be performed at each visits. If bacterial infection is confirmed, treatment with antibiotics will be administered in the opinion of the investigators/subinvestigators. The patients are not allowed to receive the injection of the investigational product until bacterial infection is negative (refer to Protocol section 7.4.6.2.Urinalysis).
 
Treatment with antibiotics will be administered to prevent bacterial infection before / after the injection of the investigational product (refer to Protocol section 6.1.2.1.Antibiotics)

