- (e) Urine culture and sensitivity is performed by the central laboratory when urinalysis (dipstick) results were suggestive of a urinary tract infection
- (f) Could be performed during the screening phase excluding diary data collection days
- (g) If the result of urine pregnancy is suspicious, investigator (or sub-investigator) is able to conduct serum pregnancy test by central laboratory.
- (h) First dose to be administered 1 (approximately 24 hours) to 3 days prior to study injection and continued for 1 to 3 days post injection (including the day of injection)
- (i) If qualification for re-treatment criteria was met, the patient will undergo the exams specified in Table 2, column marked "If qualification for re-treatment criteria was met".
- (j) Subjects who are not re-treated will remain in treatment phase 1 and continue to visit at the scheduled study visit.
- (k) Patients must have stopped medication (i.e.: anticholinergic and beta-3 adrenergic receptor agonist indicated for patients with OAB, or other medications) or therapies for OAB for at least 7 days prior to start of screening procedures
- (l) Samples may be collected during the screening period through Day 1 (prior to randomization)

**Table 2 Time and Events Table [Treatment phase 1 (if qualification for re-treatment criteria was met) to treatment phase 2]**

	Treatment phase 1	Treatment phase 2														With drawal
		1st re-treatment	Re-treatment (1st)							If qualification for re-treatment criteria was met (Within 21days prior to re-treatment)	Re-treatment (2nd)					
Week	If qualification for re-treatment criteria was met (Within 21days prior to re-treatment)		2	6	12	18 a	24 a	30 a	Study exit (48 weeks after 1st treatment)		2	6	12 a	18 a	Study exit (48 weeks after 1st treatment)	
Window	0	± 3 d	± 7 d	± 7 d	± 7 d	± 7 d	± 7 d	± 7 d	± 7 d	0	± 3 d	± 7 d	± 7 d	± 7 d	± 7 d	
Patient characteristics etc.																
Neutralizing antibody									X						X	X
Efficacy																
Check of bladder diary b	X		X	X	X	X	X	X	X		X	X	X	X	X	X
KHQ, OABSS	X			X	X	X	X	X	X			X	X	X	X	X
TBS	X		X	X	X		X		X		X	X	X	X	X	X
Safety																
Adverse events	X	X	X	X	X	X	X	X	X	X	X	X	X	X	X	X
Physical exam	X								X						X	X
Height, Weight	X c		X d	X	X	X	X	X	X	X c	X c	X	X	X	X c	X c
Vital signs	X			X	X	X	X	X	X	X	X	X	X	X	X	X

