## 9.2. Sample Size Considerations

### 9.2.1. Sample Size Assumptions

The sample size for this study is hypothesized based on the observed treatment difference in the change from baseline of the daily average number of urinary incontinence episodes and the average volume voided per micturition at Week 12 from the integrated data of studies 191622-095/191622-520. It is assumed that the mean differences in the daily average number of urinary incontinence episodes and the average volume voided per micturition between GSK1358820 and placebo are -1.79 episodes/day and 30 mL from these studies results. Using the two sample t-test, 240 subjects in total (120 subjects for each treatment group) is required to achieve at least 89% power at the two-sided significance level of 5% to detect the assumed treatment differences for the daily average number of urinary incontinence episodes and the average volume voided per micturition simultaneously when common standard deviations (SD) are 3.5 episodes/day in the daily average number of urinary incontinence episodes and 70 mL in the average volume voided per micturition. This power is calculated by using power of each endpoint and Bonferroni inequality. Using above assumed values, power is 98% for the daily average number of urinary incontinence episodes and 91% for the average volume voided per micturition at the two-sided significance level of 5%. In this case, joint power is expected at least 89% (=98 + 91 -100) calculated by Bonferroni inequality.

The minimum detectable effect (i.e., the smallest observed effect size that could be statistically significant) based on the two sample t-test is a -0.9 episodes/day in the daily average number of urinary incontinence episodes and a 17.8mL in the average volume voided per micturition, respectively, when common standard deviations are 3.5 episodes/day in the daily average number of urinary incontinence episodes and 70 mL in the average volume voided per micturition.

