8.5.3. Urinary Tract Infection (UTI)

Analyses to further characterize the AE of preferred term ‘urinary tract infection’ will be undertaken for only TC1.

CONFIDENTIAL

204947

UTI will be summarized by PVR urine volume category of maximum PVR volume in TC1 (as described in 8.5.1.), and by CIC usage in TC1 (for any reason).

Time to onset of first UTI will be summarized and analysed according to “Study Specific Safety Analyses for Time to Event data” in 8.5.2. Listing will also be prepared.

(Time to onset of first UTI) = (The date of onset of first UTI) – (the date of first treatment) + 1

For subjects who initiated CIC prior to UTI, time between the onset of the use of first CIC and (for any reason) the onset of the UTI will be summarized.

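### Extra urine cultures after raised PVR or CIC fall mostly on the active arm, and the SAP does not separate differential detection from true infection in the UTI comparison

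*Protocol*

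**What the plan says.** **Routine rule.** Protocol 7.4.6.2.1 requires a site dipstick at all study visits. Footnote (e) of the Time and Events Table says: "Urine culture and sensitivity is performed by the central laboratory when urinalysis (dipstick) results were suggestive of a urinary tract infection". Footnote (f) of Table 2 and section 7.4.6.2.2 repeat this condition.

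**Added testing.** Sections 7.4.6.2.2 and 7.4.7 add cultures without stating a dipstick condition:
- PVR 200 to below 350 mL without CIC: an extra visit one week later, at which a dipstick "as well as urinalysis, urine culture and sensitivity test at the central laboratory will be performed". A second such visit follows if PVR is increasing and CIC is not started.
- CIC start: a culture at initiation and another at a visit one week later. Then: "In addition, these tests and analyses will be performed at scheduled visits after CIC is initiated".
- CIC stop: a further visit one week later with culture.

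**A different rule.** The risk table in Protocol 4.6.1 says: "Urinalysis, urine culture and sensitivity test will be performed at each visits".

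**Event definition.** Under 7.4.6.2.2, "urinary tract infection is recorded as an adverse event, irrespective of symptoms", provided that culture shows at least 10^5 CFU/mL and leukocyturia exceeds 5 per high power field. Both are required.

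**Analysis.** The amended SAP reports UTI among the special-interest events by arm (Table 3.66 for the first 84 days). Section 8.5.3 adds UTI by CIC use and by maximum PVR (Tables 3.138 and 3.139), and states: "Time to onset of first UTI will be summarized and analysed" (Table 3.140). The model, in SAP 8.5.2, is a Cox regression on treatment and the stratification factor, giving a hazard ratio and 95% interval without a p-value.

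**The concern.** The number and type of cultures depend on PVR and CIC, which the drug itself affects. A subject in PVR or CIC follow-up has more occasions on which bacteriuria with leukocyturia can be found, and some of those cultures do not need a positive dipstick. Because symptoms are not required, a finding without clinical illness becomes an adverse event.

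Three outputs are affected. The arm difference in UTI incidence and the hazard ratio include whatever the added testing finds. The tables by CIC use and maximum PVR group subjects by the same variables that set the testing schedule, so they cannot separate detection from risk. The interval from first CIC to UTI is also shaped by the culture mandated one week after CIC starts.

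SAP section 8 leaves unscheduled-visit safety data out of the summaries, but this does not remove the effect. SAP 11.4.1.2 assigns adverse events to a phase by start date, so a UTI found at an extra visit still counts. No planned analysis is limited to symptomatic UTI or to UTI found through the routine dipstick rule.

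**Working it through.** **The plan's own figures.** The plan gives no figure for this effect. Its one design calculation concerns efficacy power (Protocol 9.2.1). It reproduces at 97.7% and 91.3%, hence 97.7 + 91.3 - 100 = 89.0%, and has no bearing on UTI.

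**Inputs from the documents (Protocol 4.6.1).** Retention: 7.1% active, 0.5% placebo. UTI: 26.4% and 10.1%, a difference of 16.3 points. Scheduled visits in the first 12 weeks: weeks 2, 6 and 12.

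**Who is affected.** Per 120 subjects, 0.071 x 120 = 8.5 on active and 0.005 x 120 = 0.6 on placebo. With 1:1 allocation, 7.1/(7.1 + 0.5) = 93% of retention cases are on active. Under 7.4.7 a retention event is one that requires CIC, so retention stands in for CIC here.

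**Ceiling for the CIC path.** If the added testing gave every such subject a UTI that would otherwise go unrecorded, the arm difference would grow by 7.1 - 0.5 = 6.6 points, or 6.6/16.3 = 40% of the earlier difference.

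**Net excess.** Compare two subjects at equal true risk over 12 weeks:
- Routine: three visits, each culture sent only after a positive dipstick.
- CIC started at week 2 and stopped within the period: five cultures without a dipstick condition (weeks 2, 3, 6, 12 and one week after stopping).

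Let q be the chance that a culture occasion meets the UTI definition and s the dipstick sensitivity. Neither is in the documents; I assume q of 2% to 20%, s of 70% to 100%, and independent occasions.

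Excess in points = 6.6 x {[1 - (1 - q)^5] - [1 - (1 - qs)^3]}

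| q | s | Routine | CIC path | Excess (points) |
|---|---|---|---|---|
| 2% | 100% | 0.059 | 0.096 | 0.25 |
| 2% | 70% | 0.041 | 0.096 | 0.36 |
| 10% | 100% | 0.271 | 0.410 | 0.91 |
| 10% | 70% | 0.196 | 0.410 | 1.41 |
| 20% | 100% | 0.488 | 0.672 | 1.22 |
| 20% | 70% | 0.364 | 0.672 | 2.04 |

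The range is about 0.25 to 2.0 points.

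**Effect of the unclear rules.** If the dipstick condition still applies at weeks 6 and 12 after CIC start, the CIC path becomes 1 - (1 - q)^3 x (1 - qs)^2. At q = 20% and s = 70% this is 1 - 0.512 x 0.740 = 0.621, and the excess is 6.6 x (0.621 - 0.364) = 1.7 points. If instead everyone is cultured at every visit, as 4.6.1 says, the s = 100% rows apply and the range is 0.25 to 1.2 points, which comes from the extra visits alone.

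**Raised PVR without CIC.** These subjects have one or two added cultures. Their share is not given. Assuming a further 5% to 15% on active and 0.5% to 1.5% on placebo, the ceiling for both groups together rises to 6.6 + 4.5 = 11.1 up to 6.6 + 13.5 = 20.1 points. The net amount is therefore left as unknown.

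**The case against.** The strongest reply is that routine surveillance is already close. Everyone has a dipstick and central urinalysis at scheduled visits. The event needs leukocyturia, for which the leukocyte esterase strip screens. A culture without a dipstick condition at a scheduled visit then adds a UTI only where the strip missed it. This stands, and the working nets out routine detection for that reason.

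Second, the wording on scheduled visits after CIC start does not expressly waive the dipstick, and footnotes (e) and (f) give no CIC exception. This also stands. The absence of a dipstick condition is clear for the extra visits and only arguable for the scheduled ones.

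Third, Protocol 4.6.1 lists elevated PVR and CIC as potential contributors to UTI, so an excess may be real. UTI is a safety outcome without a hypothesis test, and the bias runs against active, so it cannot conceal a UTI risk. These points limit the consequence; they do not make the estimate interpretable.

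Fourth, a count limited to routine detection is not truly equal testing. An infection found and treated at an extra visit may be culture-negative at the next scheduled one, and this loss would fall mostly on active. That is correct, and the restricted count should be presented as a lower bound.

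A reader might also infer that any positive culture is a UTI, or that other subjects are not cultured. The leukocyturia criterion and the dipstick rule contradict both readings.

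**Conclusion.** The concern holds as differential ascertainment of unknown size. The documents establish that testing is more intense after raised PVR or CIC, that these events are expected mostly on active, that symptoms are not needed for a UTI event, and that the SAP has no analysis separating detection from risk.

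For the CIC path the net excess is about 0.25 to 2.0 points, with a ceiling of 6.6, against 16.3 points in the earlier studies. This rests on the overseas retention rates carrying over, on CIC starting at week 2, and on the assumed yield, dipstick sensitivity and independence.

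A reader might take the chance of at least one positive in 2 to 6 extra cultures at 5% to 20% each (1 - 0.95^2 = 9.8% to 1 - 0.80^6 = 73.8%), multiply by 6.6, and conclude that testing alone adds 0.6 to 4.9 points. That is gross detection: it assumes that routine testing would have found none of these infections and that no affected subject already had a recorded UTI. The documents support neither assumption. Nor do they support attributing the earlier 16.3-point difference to testing.

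This is a worthwhile improvement to the safety analysis. It does not threaten the efficacy conclusions.

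**What to change.** In SAP 8.5.3, and beside Tables 3.66 and 3.138 to 3.140:

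1. Report by arm the number of urine cultures and of additional PVR or CIC visits per subject.
2. Classify each UTI event by how it was detected: dipstick or central urinalysis positive at a scheduled visit; found only through a culture mandated by PVR or CIC follow-up; or diagnosed elsewhere.
3. Give a supportive UTI incidence and hazard ratio that exclude events found only through mandated PVR or CIC cultures, beside the all-UTI result.
4. State that the restricted count is a lower bound, because infections found and treated at extra visits are lost differentially, mostly on active. The two counts then bracket the effect.

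In the protocol, reconcile the culture rule in 4.6.1 with footnotes (e) and (f) and section 7.4.6.2.2, and state whether the dipstick condition applies at scheduled visits after CIC start.

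The cost is one derived classification and a few supportive rows. The adverse event, laboratory and bacteriology datasets are already listed in SAP 11.13. The documents do not confirm that site dipstick results are stored, but central urinalysis at scheduled visits includes nitrite, leukocyte esterase and sediment white cells, so the dipstick condition can be approximated. The analysis changes require no change in study procedures.
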